### 5.6.1 Early Termination Study Visit

Any participant who withdraws will be contacted by the PI to be offered the opportunity to complete any outstanding assessment visits with compensation.

### **6 STUDY EVALUATIONS AND MEASUREMENTS**

### 6.1 Screening and Monitoring Evaluations and Measurements

Our pre-consent phone screening will closely parallel the phone screenings used in previous parts of this study. This has been efficient and well-tolerated by participants in a variety of housing circumstances in that study. The primary goal will be to ensure eligibility and interest in study participation. We will also ensure participant will be reachable for the 24-week study time frame. We will assess diabetes history, housing history, medication use, communication preferences/access, and also collect basic demographic data, (e.g. age, gender). See *DH Aim 3 Screener Script* for question structure.

During the baseline and follow-up assessment visits data will be collected using the following procedures:

Demographics/ Medical History	Participants will be given a verbal survey at either the Baseline 1 or Baseline 2 visit to add to data collected in pre-consent screening.				
	Topics will include: health insurance, education, medical history, and current living situation.				
Medical record request/abstraction	Signed release of information forms will be collected for participants at their primary care clinic/preferred health system and at Hennepin Healthcare and Hennepin County affiliate clinics (including Health Care for the Homeless). Once signed consent is obtained, EPIC records at Hennepin Healthcare will be directly accessed for abstraction with signed consent.				
	Release of information (ROI) forms will be collected for outside health systems patients have used. ROI forms will be sent, via secure e-mail or fax, to Health Information Management offices at outside health systems. Return of information will occur via secure file transfer system preferred by the recipient organization.				
	Returned records will be abstracted by study staff.				
	After the Baseline 1 visit, we will abstract the past 12 mo. of:				
	
 
Medication list, dose, frequency, and prescriber
 
Comorbidities (including physical and behavioral health)
 
History of medication refill frequency
 
History of hemoglobin A1c: Mo./year, results of tests
 
				
	After the follow-up assessment visits, we will review and abstract any changes in:				
	
 
Medication list, dose, frequency, and prescriber
 
History of medication refill frequency
 
History of hemoglobin A1c: Data and results of tests
 
				
Insurance company claims data	We will collect data from health insurers including Minnesota Medical Assistance. We will work directly with Hennepin County per instructions of the Minnesota Department of Human Services Medicaid office to securely obtain records at the end of the study on all participants. Signed consents will be sent via secure fax or secure file transfer process.				

	Pharmacy and health care claims data detailing medication refill patterns as well as clinic, hospital, and emergency department use across all health systems will be abstracted. We will explore the feasibility of using pre-established protocols to examine hospitalizations for hyper and hypoglycemia. 109				
Biometric data	The following biometric data will be collected from participants at baseline and both follow-up assessment visits. See Biometric Data for detailed information on how these will be measured:				
	
 
Blood pressure
 
Height
 
Weight
 
Hemoglobin A1cParticipants will receive a copy of their results. See HgA1c Result for A1c results sheet.
 
				
Medication review	Patients will be asked to bring a list of all their medications to the Baseline 2 assessment visit. All dates, doses, frequencies, and prescriber information will be recorded.				
	If patients forget, they will be asked to name this information and permission will be sought to confirm this within their medical record.				
Patient-reported survey measures	Formal assessment surveys will be collected at Baseline and follow-up assessment visits as described in Table 1.				
Satisfaction with intervention	At the 16-week assessment visit, the assessor (who is not the interventionist) will collect input about the participant's experiences during the intervention.				
	Participant satisfaction will be assessed by the Client Satisfaction Questionnaire, an 8-item measure developed in the mental health field. 95				

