Data And Safety Monitoring Plan	[name] (PI) will work closely with study staff to monitor the quality of data collected at assessment. This pilot trial (N=54), does not meet NIH criteria requiring a Data Safety Monitoring Board				

(DSMB), however Drs. [name], [name], and [name] will oversee a detailed safety monitoring plan.

TABLE 1: SCHEDULE OF STUDY ASSESSMENT PROCEDURES

Study Phase	Eligibility screening	Consent, Baseline visit #1	Run-in, Baseline visit #2	Follow-up visit #1	Follow-up visit #2
Visit Number		1	2	3	4
Study Weeks, approximate	0	1	2-3	12-16	24-30
Confirm communication preferences	X	X		X	X
Review Inclusion/Exclusion Criteria	X	X	X		
Informed Consent		X			
Demographics/Medical History/Medication List		X	X		
Medical records and insurance access permissions		X			X
Biometrics: BP, Height, Weight, Hemoglobin A1c (fingerstick/venipuncture)		X	X	X	X
Medication review		X	X	X	X
Self-report survey measures:					
Mental Health Inventory (MHI-5) 			X	X	X
Health-related Quality of Life Short Form (SF-12) 			X	X	X
Problem Areas in Diabetes (5-item PAID) 			X	X	X
Diabetes self-management questionnaire (DSMQ) 			X	X	X
Adherence to Refills and Medications Scales-Diabetes (ARMS-D) 			X	X	X
Self-reported medication adherence (Adherence Starts with Knowledge, ASK-12) 			X	X	X
Basic needs survey 		X		X	X
Lifetime housing status		X			
Current housing status, 30 day recall		X		X	X
Use of substances (ASSIST)		X		X	
Self-reported health care use (NHANES)		X		X	X
Discrimination in Medical Settings Scale 117		X			
Client Satisfaction Questionnaire (CSQ-8) 95				X	

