### 5.1.2 Baseline Assessment and Run-in

After the screening visit, after the participant's signed consent at baseline assessment visit #1, the medical record will be accessed. Participants' diabetes diagnosis, A1c results, medication list, frequency of refills, primary care team, and pattern of clinic/emergency department/hospital visits will be abstracted and recorded for the previous 12 months. If patients are found not to have diabetes at this point, they will be excluded from the study. We will also process their point-of-care A1c after visit #1 to ensure eligibility.

If patients are confirmed to be eligible based on medical record review, we will proceed with baseline visit 2 which can be done remotely or in-person.

As outlined in Table 1 above, the screening visit and baseline assessment visits will collect:

- Review Inclusion/Exclusion Criteria
- Informed Consent, HIPPA authorization
- Demographics/Medical History/Medication list
- Release of information for health systems used in last 12 mo.
- Release of information for insurance claims data in the last 12 mo.
- Biometrics: BP, height and weight, hemoglobin A1c (A1c)
  - O Alc testing involves the collection of a 1.5 μL blood sample via fingerstick or venipuncture
- Patient-reported outcome survey items (See Table 1)

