### 5.4 Concomitant Treatment

All prior and concomitant diabetes care in the year prior to the screening visit and through the end of the study will be recorded via self-report.

**5.5 Rescue Medication Administration** *Not applicable in this behavioral trial.* 

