# **6.3** Pharmacokinetic Evaluation Not applicable

# 6.4 Safety Evaluation

Subject safety will be monitored by adverse events and rates of early termination of the study. We will also follow safety protocols in case we identify dangerous blood pressure, or heart rate values at baseline or follow-up assessment visits. See Section 8 for details.

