## **7.4.2** Pharmacokinetic Analysis *Not applicable*.

### 7.4.3 Safety Analysis

We will complete quarterly data reviews to examine safety events in the intervention and comparison groups. [name] will advise us if any changes to the existing study protocol are needed to ensure patient safety.

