# 8.2 Adverse Event Reporting

Unanticipated problems related to the research involving risks to subjects or others that occur during the course of this study and SAEs will be reported to the IRB in accordance with IRB Attachment EEE: Prompt Reporting Guidelines. AEs that are not serious but that are notable and could involve risks to subjects will be summarized and submitted to the IRB at the time of continuing review. Adverse event reports will be reviewed annually with the HHRI IRB to ensure participant safety.

[name] will be responsible for completing Adverse Events Forms should an event occur. She will report Serious Adverse Events to the HHRI IRB within 24 hours of having received notice of the event.

Drs. [name], [name], and [name] will collaboratively gather any information needed to investigate any reported safety events and determine subsequent action. Any subsequent action will be documented and reported to the HHRI IRB and the Program Officer at NIH.

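### Hypoglycaemia is a plausible harm of raising diabetes-drug adherence, but it is not a named safety outcome and no identical enquiry for it in both arms is described

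*Combined protocol and SAP*

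**What the plan says.** Section 6.4 defines safety monitoring in general terms: "Subject safety will be monitored by adverse events and rates of early termination of the study". It adds a response to dangerous blood pressure or heart rate. Section 7.4.3 says "We will complete quarterly data reviews to examine safety events in the intervention and comparison groups" and names neither an event type nor a data source. Section 8.1 defers to the IRB's definitions. The risk assessment in 9.4.2 covers distress, loss of privacy and worsening mental illness.

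Low glucose appears in two places. Section 8.4 has a clinician paged if a glucose reading taken during a study visit is below 60. Section 6.1, on insurance claims, says "We will explore the feasibility of using pre-established protocols to examine hospitalizations for hyper and hypoglycemia".

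Several sources could carry information on hypoglycaemia in both arms:
- Self-reported health care use is collected at baseline and both follow-up visits (Table 1). The follow-up assessors are blinded (4.2, 5.2.8).
- Concomitant diabetes care "through the end of the study will be recorded via self-report" (5.4).
- Claims are to be obtained for all participants at the end of the study (6.1).

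Section 7.4.1 compares health care use between arms, under the efficacy analysis.

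**The concern.** If coaching works, participants take more glucose-lowering drug. The synopsis lists food insecurity among the barriers this population faces. Section 4.5.2 has three exclusions, none concerning insulin or drug class, and the synopsis limits the refill measure to non-insulin drugs, which suggests that insulin users are expected. Better adherence with irregular meals makes low glucose a foreseeable harm.

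Episodes that nobody asks about cannot be recovered at analysis. A participant who treats an episode alone, or is treated at an outside emergency department, enters the safety record only if it comes up with staff. The pilot is meant to prepare a fully powered trial (3.1). Without a defined count by arm, that trial would be planned with no stated bound on this harm.

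**Working it through.** **1. Where low glucose could be counted**

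| Place in the plan | Status |
|---|---|
| 6.4, 7.4.3, 8.1, 9.4.2 | not named |
| 8.4, reading below 60 | clinical response, only if glucose is measured in a study visit |
| 6.1, claims | feasibility look at hospitalisations only; data arrive at study end, too late for quarterly reviews |
| 7.4.1, health care use by arm | efficacy comparison, not by cause |
| Table 1, self-reported health care use | both arms, blinded; whether it records the reason for a visit is not shown |

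The plan states no hypoglycaemia rate or bound, so there is no figure to reproduce.

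**2. Does unequal contact tilt the count?**

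Contacts after randomisation, leaving out session 1 on the baseline day:
- Coaching: 9 sessions + 3 booster calls + 2 blinded visits = 14.
- Comparison: 5 calls (4.3.1), 6 (5.2.7) or 7 (Table 2), + 2 blinded visits = 7 to 9.

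Assumptions, not from the plan: event time t is uniform over weeks 0 to 24, and every later contact reveals the event with the same probability q. Sessions are evenly spaced to week 12, with boosters at weeks 16, 20 and 24. Comparison calls fall at weeks 6, 10, …, 22 (4.3.1), 4, 8, …, 24 (5.2.7) or 3, 7, …, 27 (Table 2). Visits are at weeks 14 and 27.

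Capture = 1 − mean over t of (1 − q)^(number of contacts after t).

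| q | Coaching | Comparison (4.3.1 / 5.2.7 / Table 2) | Ratio, coaching to comparison |
|---|---|---|---|
| 0.1 | 45.9% | 36.2% / 40.0% / 44.4% | 1.27 / 1.15 / 1.03 |
| 0.3 | 80.6% | 73.5% / 78.4% / 83.2% | 1.10 / 1.03 / 0.97 |
| 0.5 | 92.8% | 88.6% / 92.5% / 95.3% | 1.05 / 1.00 / 0.97 |

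At q = 0.8 the ratios are 1.00 to 1.02. If each session is attended with probability 0.5 (the 7.1 benchmark), the ratio runs from 0.92 to 1.13. The ratios straddle 1. At low q, more than half of events are missed in both arms, which is the larger loss.

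**3. What a question at the blinded visits adds**

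Assume that 75% attend both visits and 25% attend neither, and that 80% of those with an episode disclose it when asked. At q = 0.1, capture rises from 44% v 34–42% to 78% v 75–78%.

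**4. What the count could show**

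There are 54 participants allocated 1:1, so 27 per arm. At the 75% follow-up benchmark, 0.75 × 54 = 40.5, about 20 per arm.

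One-sided 95% upper limit with no event = 1 − 0.05^(1/n):
- n = 27: 10.5%
- n = 20: 13.9%

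Exact unconditional (score-statistic) 95% CI for the risk difference, in percentage points:
- 0/27 v 0/27: −13.6 to +13.6
- 0/20 v 0/20: −18.2 to +18.2
- 1/27 v 0/27: 3.7 (−9.9 to 19.0)
- 2/27 v 0/27: 7.4 (−6.2 to 24.3)

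Chance of at least one event in an arm of 27 = 1 − (1 − p)^27. For assumed true rates of 2%, 5% and 10% this is 42%, 75% and 94%.

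**The case against.** The strongest reply is that this is a 54-person pilot expected to be classed as minimal risk. Staff change no prescriptions (4.1.2), and entry requires A1c of at least 7.5%. Section 8.4 has a low-glucose response, and hypoglycaemia can still be reported as an ordinary adverse event. The full questionnaire and the IRB definitions are separate documents and might already contain an enquiry. All of this stands. It lowers the priority and makes the fix conditional on the questionnaire. It does not supply a defined count by arm.

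Four stronger readings are tempting, and the documents do not support them.

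- *Extra contact will make coaching look more harmful.* The ratios above fall on both sides of 1 and rest on an assumed q that is the same for a coaching session and a contact-details call.
- *Hospital and emergency visits stop being abstracted from charts after baseline.* Section 5.1.2 says the "pattern of clinic/emergency department/hospital visits will be abstracted and recorded for the previous 12 months", and the 6.1 list introduced by "After the follow-up assessment visits, we will review and abstract any changes in" omits such visits. But the baseline list in 6.1 omits them too, so absence from that section's lists shows nothing.
- *The quarterly review rests only on events that staff happen to hear about.* Section 8.2 says "She will report Serious Adverse Events to the HHRI IRB within 24 hours of having received notice of the event". That sets a deadline for reporting to the IRB; it does not say what feeds the review.
- *These sources have no analysis by arm.* Section 7.4.1 does compare health care use. What is missing is the cause and the safety label.

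**Conclusion.** The point holds in limited form. The plan gives good reason to expect hypoglycaemia as a possible harm, yet does not name it as a safety outcome, and the visible text describes no identical enquiry in both arms. The likely cost is under-counting in both arms; a difference between arms cannot be signed and is probably small. Even a complete count would be descriptive: 0/27 leaves rates up to 10.5% open, and 0 v 0 leaves a risk difference of up to 13.6 points either way. The capture figures are illustrations under an assumed q. The conclusion also assumes that the unseen questionnaire has no such item; if it has one, only the reporting gap in 7.4.3 remains. No primary endpoint or feasibility criterion changes. Priority is low to moderate.

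**What to change.** 1. Unless the questionnaire already has one, add one identically worded hypoglycaemia question at both existing blinded follow-up visits. For example, ask about any episode since the last assessment that needed another person's help, emergency care or hospital.
2. In 7.4.3, report by randomised arm the number asked, the number with an episode, and the risk difference with exact 95% CI. Present it descriptively, with no test.
3. If the 6.1 claims coding proves feasible, add hypoglycaemia hospitalisations by arm, kept separate from hyperglycaemia. Use one fixed window for everyone (for example randomisation to week 24) and state the number with obtainable claims. Say that this bounds hospitalised events only. If the coding does not work, say so.

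The cost is one survey item by amendment, a few sentences in 7.4.3, and diagnosis coding of claims already planned; no new visit is needed. The limits are sparse events, recall error, and no answer from people who attend neither follow-up (up to 25% at the 7.1 benchmark). Claims miss self-treated episodes and people without claims, and arrive only at study end.

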### **6.2** Efficacy Evaluations

Although our study is not fully powered to detect efficacy, we will collect the following eventual efficacy measures to prepare for later, fully-powered testing at baseline and both follow-up assessment visits (Table 1):

- Hemoglobin A1c (primary)
- Adherence to diabetes medications (ARMS-D) (secondary)
- Adherence to all medications (ASK-12) (secondary)
- Diabetes self-care (DSMQ) (secondary)
- Difficulties with diabetes management (PAID) (secondary)

# **6.3** Pharmacokinetic Evaluation Not applicable

# 6.4 Safety Evaluation

Subject safety will be monitored by adverse events and rates of early termination of the study. We will also follow safety protocols in case we identify dangerous blood pressure, or heart rate values at baseline or follow-up assessment visits. See Section 8 for details.

#### 7 STATISTICAL CONSIDERATIONS

# 7.1 Primary Endpoint

The primary endpoint of this study is the satisfaction of participants in this pilot randomized trial (via CSQ-8).

The feasibility and acceptability of study protocols for recruitment, retention, and randomization are also important. We will assess this by measuring our ability to recruit and retain participants, and the assessment and treatment visits we can deliver (i.e., participant's attendance and follow-up with scheduled sessions and treatment activities). In addition to above outcomes, we will carefully track the number and types of between-treatment communications with participants (who initiated communication; form of communication: text, calls, e-mails, etc.).

We will consider the study feasible if we enroll 75% of those screened who meet inclusion criteria, and 75% of enrolled participants complete at least one follow-up. We will consider 50% session attendance as indicative of feasibility. We will consider the intervention acceptable if 70% of participants are satisfied and would recommend it to others.

We will also analyze our primary clinical endpoint of change in A1c between intervention and comparison groups between baseline follow-up visit #1 (approx. 12-16 weeks)

if it changes from baseline to between intervention.

# 7.2 Secondary Endpoints

Secondary endpoints will include the following changes from baseline to follow-up visit #1 (approx. 12-16 weeks) between intervention and comparison groups.

- Psychological wellness (SF-12, MHI-5)
- Adherence to diabetes medications (ARMS-D) (secondary)
- Adherence to all medications (ASK-12) (secondary)
- Diabetes self-care (DSMQ) (secondary)
- Difficulties with diabetes management (PAID) (secondary)

Secondary endpoints will also include change from baseline to follow-up visit #2 (approx. 24-30 weeks) of A1c to assess sustained change of our primary endpoint.

We will also complete exploratory analyses on the change from baseline to follow-up visit #2 of:

- Adherence to diabetes medications (ARMS-D)
- Adherence to all medications (ASK-12)
- Diabetes self-care (DSMQ)
- Difficulties with diabetes management (PAID)

Exploratory analyses will further measure changes from baseline to follow-up visits #1 and #2 of other self-reported and claims-measures will be assessed including housing status, substance use, and other biometric measures (BP, BMI). Exploratory analyses will also compare self-reported adherence measures (ARMS-D and ASK-12) to measures built from medication refill patterns in insurance claims.

#### 7.3 Statistical Methods

Statistical support for this trial will be provided by [name] and [name] via the Biostatistical Design and Analytics Center (BDAC) at UMN.

#### 7.4 Baseline Data

Baseline and demographic characteristics will be summarized by standard descriptive summaries (e.g. means and standard deviations for continuous variables such as age and percentages for categorical variables such as gender).

# 7.4.1 Efficacy Analysis

We will use summary statistics (mean, standard deviation) to examine CSQ-8 scores for all participants. We will use t-tests to examine the differences in CSQ-8 scores between the intervention and comparison groups; we hypothesize no difference. We will also examine the experiences of White vs. Black, Native American, and Hispanic participants. We will also generate summaries of the age, gender, and race/ethnicity of people at the highest and lowest quintiles of CSQ-8 scores.

We will use generalized linear models to compare changes in A1c and medication adherence (ARMS-D and ASK-12) over time in intervention vs. comparison groups. We will control for baseline differences and changes in housing status over time. Adherence will also be examined with pharmacy refill data which we will compare to self-report (ARMS-D and ASK-12). We will use an intention-to-treat approach including all randomized participants; multiple imputation will generate data for those lost to follow-up. Similar modeling approaches will compare psychological wellness, blood pressure, and health care use outcomes.

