### 4.2 Allocation to Groups and Blinding

Participants will be randomized to either the intervention or a control group (1:1). Randomization will be stratified by housing type (unstable (e.g., shelter, staying outside) vs.

more stable (e.g., worry about rent payment, supportive or transitional housing)). Randomization will occur after baseline assessment visit #2 via REDCap. Staff who conduct who conduct the follow-up assessment visits will be blind to condition.

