# 4.3.2 Total Number of Study Sites/Total Number of Subjects Projected

Enrollment for the study will continue until 54 participants have been enrolled.

HHRI will serve as the only site for this study.

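### Age and gender are related to satisfaction only through profiles of the top and bottom CSQ-8 quintiles (about 8 to 10 people each); a summary in all respondents, allowing for arm, would use the data better

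*Combined protocol and SAP*

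**What the plan says.** Section 7.1 sets the endpoint: "The primary endpoint of this study is the satisfaction of participants in this pilot randomized trial (via CSQ-8". Table 1 schedules CSQ-8 once, at follow-up visit 1. Section 6.1 describes it as an 8-item measure.

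Section 7.4.1 then lists four uses of the score:

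- an overall description: "We will use summary statistics (mean, standard deviation) to examine CSQ-8 scores for all participants";
- a t-test between arms, with no difference hypothesised;
- a look at race and ethnicity: "We will also examine the experiences of White vs. Black, Native American, and Hispanic participants", with no method given and no restriction to quintiles;
- the extreme-group profile: "We will also generate summaries of the age, gender, and race/ethnicity of people at the highest and lowest quintiles of CSQ-8 scores".

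For the profile the plan names no test, no measure of precision, no rule for tied scores and no separation by arm. Section 4.3.2 fixes the size: "Enrollment for the study will continue until 54 participants have been enrolled". The retention target in Section 7.1 is that "75% of enrolled participants complete at least one follow-up". Section 7.5 gives no effect size, standard deviation or power.

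**The concern.** A quintile profile selects people on the outcome and then describes who they are. Three things follow.

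- The middle three fifths of respondents contribute nothing, and each remaining group is so small that its percentages are hard to interpret.
- An 8-item score produces ties, so the cut can fall among people with the same score. Group membership is then arbitrary, or the groups grow and become unequal.
- As written, the quintiles pool two very different programmes: ten coaching sessions, or one education session of 15 to 30 minutes. If satisfaction differs by arm, the top and bottom groups partly describe allocation.

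At stake is how well the pilot can describe who found the programmes satisfactory, using data that it collects anyway. This matters most for age and gender, which have no other planned analysis against CSQ-8.

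**Working it through.** The plan gives no figure for this analysis, so there is none to reproduce.

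**Group sizes.** Inputs: N = 54 (Section 4.3.2) and retention of 75% (Section 7.1 target) to 100%.

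- Respondents: 54 × 0.75 = 40.5, taken as 41; 54 × 1.00 = 54.
- One quintile: 0.20 × 40.5 = 8.1; 0.20 × 54 = 10.8. In whole people, 8 and 10.
- In neither group: 0.60 × 40.5 = 24.3; 0.60 × 54 = 32.4.

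The retention target counts anyone with at least one follow-up, but CSQ-8 is taken only at visit 1. The number of respondents could therefore be below 41 even if the target is met.

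**Precision of a percentage.** Exact (Clopper-Pearson) 95% interval for an observed 50%:

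- 4 of 8: 16% to 84%.
- 5 of 10: 19% to 81%.

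**Information lost.** Simulation with at least 3,000 runs per case. Assumptions, none of them in the documents: normal score, trait split 50/50, two-sided 0.05. All respondents: t-test of the score by trait. Quintiles: Fisher's exact test of the trait, top against bottom. Ranges are the spread over separate runs.

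| True difference | n | All respondents | Quintiles (Fisher) |
|---|---|---|---|
| 0.8 SD | 41 | 68% to 71% | 42% to 46% |
| 0.8 SD | 54 | 82% to 83% | 48% to 50% |
| 0.5 SD | 41 | 34% to 35% | 16% to 19% |
| 0.5 SD | 54 | 43% to 44% | 17% to 18% |

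Fisher's test is conservative in groups this small. With no true difference it rejects in about 2% of runs at n=41 and 1% to 2% at n=54, against 5% for the t-test. With the mid-p version at n=54 and 0.8 SD, the quintiles reach 67% to 68% against 82%. About half of the n=54 gap therefore comes from the choice of test. At n=41 the gap remains (about 45% against 70%).

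**Continuous age.** Assumed correlation with CSQ-8 of 0.3; Pearson test in everyone, t-test of age between the end quintiles:

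- n=41: 48% against 36%.
- n=54: 61% against 45%.

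**Ties.** Assumed whole-number scores with mean 27, SD 4.5 and range 8 to 32. The top cut falls inside a block of tied scores in 67% (n=41) to 73% (n=54) of runs. If tied people are all kept, the groups average about 10 people at n=41 and 13 at n=54.

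**Arm mixing.** If the arms differ by an assumed 0.5 SD, the top quintile is on average about two thirds coached (67% to 68%) and the bottom about one third (33% to 34%). At 0.3 SD the shares are about 61% and 39%. With no arm difference both are 50% on average.

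**The case against.** The strongest reply is that this is one descriptive line in a pilot that calls itself under-powered for efficacy. No test is planned on the quintiles, so power figures apply a yardstick that the plan never used. That stands: the figures show how much information is set aside, not the failure of a planned test. The wide intervals for 8 or 10 people do not depend on any test.

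A reader might infer that the plan studies satisfaction by demographics only through the quintiles. The documents do not support that. Section 7.4.1 separately plans a comparison of White participants with Black, Native American and Hispanic participants that is not confined to the extremes. The point stands in full only for age and gender.

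A reader might also infer that real differences will often be missed because of the quintiles. That depends on effect sizes and an alpha level that the documents do not give. The sample size is itself a major limit: at 0.5 SD the analysis of all respondents would still miss 56% to 66%.

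Finally, the plan hypothesises no arm difference in CSQ-8, and under that hypothesis the arm mixing averages out. The concern about mixing is therefore conditional. The same paragraph tests for an arm difference, however, so the plan treats one as possible.

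**Conclusion.** The point holds as a minor improvement. For age and gender, the planned description of who is satisfied rests on two groups of about 8 to 10 people, leaves out about 60% of respondents, has no tie rule and does not separate the arms. Using all respondents was more informative at every effect tried. The size of the gain rests on assumed effects and on the test used. At 0.8 SD it is about 25 percentage points at n=41. At n=54 it is 14 to 15 points with mid-p (82% less 67% to 68%) and 32 to 34 with Fisher (82% less 48% to 50%). For age at a correlation of 0.3 it is 12 to 16 points (48% less 36%; 61% less 45%).

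It would be wrong to conclude that the pilot's acceptability finding is at risk. Section 7.1 judges acceptability by whether 70% of participants are satisfied and would recommend the intervention. No feasibility or acceptability criterion uses the quintile summary.

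**What to change.** In Section 7.4.1, add an exploratory summary of CSQ-8 in all respondents:

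- mean CSQ-8 with 95% CI by gender and by race/ethnicity, and the slope of CSQ-8 on age with 95% CI (age kept continuous if possible), each from a simple linear model that includes arm;
- the same model as the stated method for the White versus Black, Native American and Hispanic comparison, with the categories defined beforehand;
- the number of respondents behind each estimate.

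The quintile profile may stay as a purely descriptive supplement. If it does, state how ties at the cut are handled and show how many people in each quintile come from each arm.

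The cost is a change of wording, a few definitions, and one extra table or model on data already collected. Intervals will remain wide at N = 54, especially for small race/ethnicity groups, so the results should be labelled exploratory and read as estimates and not as tests.
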